## Potential Risks

Risks associated with the proposed study are minimal because discussing thoughts and feelings regarding the HPV vaccine generally promotes good health, not endangers it. The only identified risks are that patient confidentiality could be breached, leading to a third party gaining access to personal health information, or that participants might experience psychological stress if questions asked as part of the study make them uncomfortable. There may possibly be other side effects that are unknown at this time. If a patient reports any other side effects, they will be recorded as an adverse event and the IRB will be notified. Methods for protecting against these risks are described below. Patients who choose not to participate will continue to receive their usual care from their primary care provider.

## Special Precautions

Each member of the project research team will be required to undergo extensive project training, in addition to standardized conduct of research and human subject protections certification required by UT Southwestern and Parkland Hospital. Project training sessions will include the following components that will be fully described in a training manual: 1) project rationale and overview; 2) detailed information about interviewing techniques and audio-recording protocols; and 3) the importance of collecting data free from bias. Research staff and the project manager will also be trained to document and report any deviations from the protocol, adverse events, or unusual

responses immediately to the PIs. The project manager and the Principal Investigators will monitor data collection procedures on a regular basis for quality assurance purposes. Evaluation checklists will be used to assess data quality and adherence to study protocols.

Once data collection begins, we will have weekly research team meetings that will include the investigators, project manager, and research assistants to discuss project implementation, address questions or concerns that might arise, and monitor recruitment and enrollment. Research assistants, the project manager and the PIs will record, review and discuss any unusual events, such as deviations from protocol or adverse events that have occurred since the last meeting. Decisions will be recorded in meeting minutes.

We do not anticipate any real harm to patients, but adverse events will be monitored. Potential adverse events for this project are all non-medical in nature. Should a parent participant become distressed during observation or interviews, the usual standard of care within the site practice will be employed. That is, the research assistant, who will be trained to detect psychological distress, will refer the participant to a designated clinic nurse, just as care takes place for any patient in the practice. Adverse event forms will be used to report all unanticipated events. The following information will be included in the report: date of event, attribution to intervention, and outcome of adverse events. Unanticipated adverse events will be reported within 7 days. Reports will be submitted via overnight courier or facsimile to the IRB, the Cancer Center's Protocol Review and Monitoring Committee, and the National Institutes of Health. A written follow-up will be submitted within 30 calendar days. All adverse events (serious or not, related or unrelated, anticipated or unanticipated) will be reported in the annual progress reports to the aforementioned groups.

Parallel procedures will be in place to monitor psychological distress or discomfort among providers. Parkland promotes an active quality improvement culture and we expect staff will engage this study in that light. In comparable studies, our investigators have found that providers generally responded well to these research procedures and have not had any adverse events.

## Procedures to Maintain Confidentiality

As described above, the most important risks to participants are threats to privacy and confidentiality. Participants will be informed that all data are completely confidential, except in cases required by law to break confidentiality. All data will be identified by a unique study ID, rather than by any identifying information. The code that links participant ID to identifying information will be stored separately from other study data, and will be accessible only to trained research staff who are directly involved with running the project. Identifiers will be destroyed after 12 months. Paper copies of data (e.g., transcripts) will be stored in locked filing cabinets, while electronic data will be stored in secure password-protected computer files. Research participants will also be informed they can refuse any questions that they do not wish to answer, and they can withdraw from the study at any time. All research staff will be trained in the appropriate safeguarding of confidential data and in the protection of human subjects as required at each study site (e.g., human subject's protection, HIPAA regulations).

All reports and data transactions within and between Parkland and UTSW subsystems will run through controlled, secure transactions to ensure the preservation of database integrity and privacy. Once the data have been transferred to the network, they will be available for integration into other statistical and database applications (e.g., SAS or MS Access) designed to support this study. All study data will be backed up on a nightly, monthly, and biannual schedule. Nightly backups recycle every 30 days. Monthly and biannual backups will be kept on static media throughout the duration of the study and up to 5 years after. Restoration requests will be routed through the IR Call center. The process of restoring data from a backup will be conducted to preserve as many data as possible, while ensuring that database integrity has been preserved.

Server hardware will have built-in redundant systems. A systems administrator will monitor server hardware, operating system and database service performance. Workstations, laptops, and other devices will receive periodic maintenance to ensure high performance and secure operation. The primary database engine will be a SQL Server. Automated processes will be monitored daily. The system will be configured to notify systems administrators if an automated process fails to run successfully.

In the unlikely event of loss of patient confidentiality, we will have a procedure in place for responding in timely

and appropriate manner. The study participant who experiences loss of confidentiality will be informed by the study principal investigators ([name] or [name]) in writing and by phone of the loss of confidentiality. Parkland clinical leadership, the IRB and NIH will be informed in the case of such an event.

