### Measurement of Primary Outcomes:

Our primary quantitative outcomes will be change in parents' HPV vaccine intentions (Aim 2) and adolescent HPV vaccine uptake (Aims 1-3). Medical records will be reviewed after 12 months to ascertain HPV vaccine status. Medical records will also be reviewed for receipt of three other adolescent vaccines (TDAP, MCV4, and influenza) as well as number and location of primary care visits in the 2 years prior to study participation.

The baseline survey will be administered to all enrolled parents (n=369) after or at the end of the recruitment call by a trained research assistant (RA), except for Aim 3 participants. The self-persuasion interview data (Aims 1A & 2), exit interviews (Aims 1-3), and audiorecorded parent-provider discussions (Aims 1B & 3) will be collected in-person by a trained RA.

Change in parents' HPV vaccine intentions (Aim 2) will be collected through the iPad application.

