### Data Management

Drs. [name] and [name] will oversee the data collection process. A Microsoft SQL Server database stored on a secure UTSW server and accessed with a Microsoft Access Data Project user interface will house the data. Several procedures will be used to maintain data integrity and ensure that data shared between Parkland and UTSW are

secure. [name] will conduct audits to assure appropriate safeguards of participant privacy are maintained. Study team personnel will send the MRNs of the most recent subjects randomized who were not eliminated at the clinic visit and were consented back to Parkland so these persons will continue to be included in the reports of study participants.

Drs. [name] and [name] will work with the project manager to oversee the data collection process and training of project staff. Project staff will undergo extensive training, using protocols developed in our prior work. A two-day training session will include: (1) project rationale and overview; (2) detailed information on data collection procedures, (3) training and certification in protection of human subjects, confidentiality and HIPAA regulations, and (4) role playing for administering interviews or hands-on practice in retrieving records data, depending on job description. Telephone interviews will be digitally recorded for quality assurance; all recordings will be reviewed during the first two weeks and a random sample will be reviewed thereafter.

For a description of the statistical analyses, see Biostatics section.

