## Criteria for Exclusion of Subjects

Age was restricted to 9-17 based on clinical guidelines and eligibility for free vaccines through the VFC program (i.e., eliminating cost as a barrier), and parental consent being required for vaccines. We will exclude pregnant adolescents due to contraindication and parents who do not provide informed consent, lack telephone access, or have impaired hearing or speech (i.e., cannot complete study activities). Parents who participate in Stage 1 or 2 will be excluded from later stages.

For Aim 2 and Aim 3, we will select adolescents who have been seen or those with upcoming appointments at any of the Parkland neighborhood and school clinics. Table 3 summarizes the inclusion and exclusion criteria for the study.

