**Primary, quantitative outcomes – HPV vaccine uptake:** We hypothesize that exposure to the self-persuasion intervention will increase 1-dose and 3-dose HPV vaccine coverage rates. We will use the EMR to measure vaccine uptake. These data will help estimate effect sizes of the self-persuasion intervention, compared to the information-only group, guiding the design and sample size for the subsequent efficacy RCT. We will also measure HPV vaccine-specific measures of intentions, benefits, and barriers .

**After completing Stage 3,** we will have quantitative and qualitative data to determine whether our self-persuasion intervention is feasible and acceptable across clinics – data that will guide us in refining intervention and measurement procedures. Thus, at the end of this stage, we will have a well-characterized and feasible intervention promoting HPV vaccination ready to be tested in future efficacy trial.

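### Does destroying identifiers after 12 months cut the link needed for the 12-month review of vaccine uptake?

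*Combined protocol and SAP*

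**What the plan says.** Procedures to Maintain Confidentiality identifies all data by a study ID and adds that "The code that links participant ID to identifying information will be stored separately from other study data". The code is open only to trained staff running the project. Soon after comes "Identifiers will be destroyed after 12 months", with no start point and no separate rule for the code. The same section backs up all study data and says "Monthly and biannual backups will be kept on static media throughout the duration of the study and up to 5 years after".

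Measurement of Primary Outcomes makes adolescent vaccine uptake a primary quantitative outcome for all three aims and says "Medical records will be reviewed after 12 months to ascertain HPV vaccine status". That clock has no stated start either. The Aim 3 analysis plan says "We will use the EMR to measure vaccine uptake" and uses the result to estimate effect sizes for the later efficacy trial.

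Two other places depend on knowing who took part. Data Management returns record numbers of randomized, consented subjects to Parkland "so these persons will continue to be included in the reports of study participants". Criteria for Exclusion of Subjects says "Parents who participate in Stage 1 or 2 will be excluded from later stages", and Table 3 gives the study database as the source for that check.

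**The concern.** The same figure, 12 months, governs both destruction of identifiers and the review that needs them. Outcome data sit under a study ID, so vaccine dates from the medical record can be tied to randomized arm or survey answers only through the linking code. If the destruction clock started at each enrolment, the code would fall due for destruction on the first day the 12-month review was due. Any delay in the review would then come too late, and a destroyed key cannot be rebuilt.

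At stake would be the Stage 3 comparison of uptake between self-persuasion and information only, which is meant to inform the size and design of the efficacy trial. A lost key could also make it harder to recognise Stage 1 and Stage 2 parents when later stages recruit.

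**Working it through.** The plan gives no figure to reproduce here. The check sets the two clocks side by side.

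**Inputs from the documents.** Destruction: 12 months after an unstated start S. Review: 12 months after an unstated start, taken here as enrolment E, plus a lag L. Enrolment: 53 (Aim 1a) + 53 (Aim 1b) + 168 (Aim 2) + 95 (Aim 3) = 369. The Project Timeline covers five years.

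**Condition for losing a link.** The code must be destroyed on its due date, and that date must precede the review: S + 12 < E + 12 + L, that is, S < E + L.

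**Result by assumed start of the destruction clock:**

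- *Each enrolment (S = E).* The margin is 12 − 12 = 0 months. Nothing is lost if L = 0; a link is lost whenever L > 0.
- *Phone consent, with the review counted from the later study visit (Aims 1 and 2).* The margin is negative by the interval from consent to visit.
- *Study start.* Identifiers would go at the end of Year 1 of five. Anyone enrolled after study start would reach the 12-month review too late.
- *Last Stage 3 enrolment.* Assuming even accrual over D months, the number lost is 95 × L / D:

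| Assumed D (months) | L = 1 month | L = 3 months |
|---|---|---|
| 6 | 15.8 | 47.5 |
| 12 | 7.9 | 23.8 |
| 18 | 5.3 | 15.8 |

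- *Study end, or completion of the record review.* None is lost.

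**Which reading is reasonable.** Both sentences place their action after 12 months. The adverse result treats the first as a fixed deadline and the second as an earliest date. Read alike, they set no order between the two actions. The study-start reading defeats the plan's own primary outcome for almost everyone, and the enrolment reading leaves it no working time. A team carrying out this protocol would hardly adopt either. The ordinary reading is that the 12-month review is completed and identifiers are then destroyed.

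**How much analysis depends on the link.** All 369 records are to be reviewed, but the written analyses are narrower. The Aim 1 plan has no analysis of follow-up uptake. In the Aim 2 plan, the paragraph on vaccination rates uses eligibility data, and the primary outcome is change in intentions, collected through the tablet application. Sources of Research Material ties vaccine status after exposure to Aim 3. Only Stage 3, with 48 + 47 = 95 parents, has a written comparison of follow-up uptake.

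**Exclusion of earlier participants.** Stages 1 and 2 hold 53 + 53 + 168 = 274 parents. Recognising them needs identity only, not study ID or arm. The record numbers returned to Parkland plausibly serve for the 168 randomized in Stage 2, less clearly for the 106 in Stage 1. The stage dates cannot be read from the timeline as supplied, so a count of parents who might go unrecognised would rest on invented calendars. None is given.

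**The case for a change.** The strongest case for acting is that the loss would be irreversible and the remedy is short. Nothing in the text provided tells staff to wait, and waiting could be seen as breaking a confidentiality commitment. The apparent safeguards are incomplete. The return of record numbers mentions neither study ID nor arm and, read literally, covers only randomized subjects. The text does not say whether the backups hold the linking code; if they do, destruction at 12 months is not achieved, and if they do not, they cannot restore the link.

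Much of this stands as a reading of the text. The start point is missing, the code is not expressly exempt, and neither the backups nor the Parkland reports can be relied on to preserve the link to arm. A clearer sentence would do no harm. What does not stand is the step from silence to lost data. That step needs the people responsible for the primary outcome to destroy the key before they have read the outcome, on a start point the protocol never states. The consent and HIPAA pages are not in the text provided, so a start point may be given there.

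**Conclusion.** No change is needed. The retention sentence leaves out a detail that the study team would fill in the obvious way: finish the 12-month record review, then destroy the identifiers. On that reading, or with the clock run from study end, the expected loss is 0 links and the planned analyses are unaffected.

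On the adverse readings, the consequence for a written analysis is confined chiefly to the 95 Stage 3 records and a pilot estimate of effect size. The partial-loss figures above rest on assumed accrual periods and review lags. The conclusion rests on two assumptions: that destruction is not carried out mechanically while outcome abstraction is open, and that no consent or HIPAA wording fixes an earlier date.

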## Potential Benefits

Parents of patients: This study offers no direct benefit to research subjects identified through the EMR for participation in surveys/interviews. Some parents of patients may find indirect benefit from identifying their reasons in favor of the HPV vaccine and their concerns, which may enable them to have more productive discussions about the HPV vaccine with their child's provider.

Providers: This study offers no direct benefit to providers although some may find indirect benefit if participation enables subjects to understand and address issues with the delivery of the HPV vaccine and discussions with parents.

Our innovative mixed-methods approach will elucidate basic mechanisms of self-persuasion, identify the optimal method for eliciting self-persuasion in an underserved population, and provide key information about factors that contribute to HPV vaccine decision-making among parents. We expect that findings will help address needs of disadvantaged populations served by safety-net healthcare systems. It will also generate evidence for intervention feasibility and acceptability that positions our interdisciplinary team to conduct a future efficacy intervention trial for underserved, undecided parents of adolescents at risk for HPV-related cancers.

## Biostatistics

Drs. [name] and [name] will work with Drs. [name] and [name] at UT Southwestern to run the quantitative and qualitative analysis for each specific aim. We will use SAS 9.3 (SAS Institute, Cary, NC) to conduct all of the statistical analyses described below.

### Aim 1. Characterize the content and scope of: a) parents' self-generated HPV vaccine arguments and b) parent-provider HPV vaccine discussions.

**Analysis Plan for Aim 1a:** Drs. [name], [name], and [name] will develop a scheme to code participants' self-generated arguments for topic (e.g., cancer prevention, HPV threat), length, number, and time to generate each; they will also create codes for argument clarity, comprehension, distinctions among arguments, and clarity of argument choices. Through an iterative process, investigators will use codes and participant ratings to examine (1) range of topics, (2) which argument topics are the strongest, (3) how many strong arguments parents are likely to generate, and (4) distribution of time spent verbalizing each argument. We will also examine the outcomes by adolescent sex to ensure we select arguments for Stage 2 that are relevant to boys and girls. Two RAs will apply the coding scheme; coding discrepancies will be resolved through consultation with Drs. [name], [name], and [name]. Drs. [name] and [name] will be consulted before proceeding to Stage 2.

In partnership with [name], a co-investigator on this project and in preparation for our large scale efficacy trial, we will analyze a subset of our existing data for Stage 1a of our project. Using our existing data, we will analyze the patterns of HPV vaccine dosing and adherence for 9-17 year old patients and stratify by race/ethnicity and sex.

### Analysis Plan for Aim 1b:

**Coding and Analyses of Audiorecordings.** We will modify [name]'s Active Patient Participation Coding scheme, a well-validated observational tool for behavior coding, to code audiorecordings of parent and provider participation in HPV vaccine discussions. [name], a recognized health communication expert will consult with the team on categories relevant to parents' participation about immunizations. We will measure both parent and provider communication outcomes.

For parents, three types of *active* communication will be captured—1) asking questions, 2) assertive expressions (offering preferences, making a request), and 3) expressing concerns (worries, seeking reassurance). Active

“verbalizations” are those that influence discussion content and provider’s beliefs and behaviors. Drs. [name], [name], and [name] will train RAs how to assign verbal utterances according to the categories above. Summary scores of the total number in each category per patient per interaction will be generated. Statements to both nurses and physicians will be counted, as nurses are often involved in vaccine discussions. We will use the phrasing used by parents to inform the content of arguments in Stage 2. For example, parents may express important values (e.g., best interest of my child), concerns, or hesitations that can help us craft relevant, easy to understand arguments.

For providers, we will assess: 1) vaccine recommendations; 2) provision of information about immunizations and HPV vaccine (three types of utterances: description, benefits, and risks); 3) partnership building (open-ended questions encouraging patients to share opinions, feelings, ask questions, and participate in decision-making); and 4) supportive talk (verbal statements of reassurance, empathy, or sensitivity).

Coders will co-code 5 recordings to establish rating agreement, and will code 3 more recordings semi-independently engaging in discussion to resolve differences. To evaluate inter-coder reliability, we will use Krippendorf’s alpha, a measure of agreement that allows for the analysis of categorical and continuous variables in the presence of missing data. To describe the communicative environment, we will compute means, standard deviations, and ranges of parent and provider communications. To explore the effect of provider discussions, we will compare parents’ responses to baseline and exit survey items regarding vaccine benefits and barriers (decisional balance), and post-visit perceived involvement in care.

**Qualitative Data Analysis.** Interviews will be audiotaped and transcribed. Drs. [name], [name], and [name] will perform in-depth analysis of all transcripts using NVivo 9.0 (QSR International). Data will be analyzed within and across transcripts. Through iterative coding and interpretation, the team will code actual utterances, expressions and concepts against participant characteristics to identify themes and relationships. We will organize these codes into a codebook that relates data to behavioral theory. Regular meetings will enable the team to test emergent themes and interpretation against the knowledge base of experts in pediatrics (e.g. [name], [name]), self-persuasion ([name]), vaccination ([name]), and intervention development ([name]).

**At the end of Stage 1, we will know:** (1) the range of pro-vaccine arguments underserved parents generate, (2) which arguments are easiest to generate, most prevalent, and persuasive, and (3) range and degree to which parents participated in HPV vaccine discussions. We will also know which peer-generated arguments are rated as clear, comprehensible, and distinct from other arguments. With these data, we will select the most prevalent argument topics with easy-to-generate arguments for the self-persuasion intervention conditions in Aim 2. Baseline descriptive information about the communicative environment will be compared with parent-provider discussions after exposure to the optimal self-persuasion intervention in Aim 3.

**Aim 2. Develop 4 self-persuasion intervention conditions (based on Aim 1 results) that vary by cognitive processing level (parents verbalize vs. listen to arguments) and choice of argument topics (parents choose vs. are assigned topics) and (b) identify which intervention condition is optimal through a controlled proof of concept study that quantitatively examines basic self-persuasion mechanisms (cognitive processing, choice) and qualitatively explores experiences with intervention tasks.**

